- ^h Vital signs include weight, temperature (oral, rectal, or tympanic), and respiratory rate. Postural vital signs (supine and standing) include pulse rate and systolic and diastolic blood pressure. At all visits, postural vital signs must be obtained after participants have been in a supine position for at least 2 to 3 minutes, followed by a standing position for at least 1 minute.
- ⁱ Clinical laboratory tests consist of clinical chemistry, hematology, and urinalysis. All laboratory tests requiring blood draws should be collected at the same time.
- ^j Urine pregnancy test will be performed in female participants of childbearing potential at Visit 1 and Visit 2 prior to dosing and at Visits 4 to 7 during study intervention. To continue in this study, a negative urine tests must be documented at Day 1 Visit (Visit 2) to start study intervention and at Visits 4 to 6 to continue study intervention. LIN-MD-64 completers who enroll in this study on the same day do not need to repeat the urine pregnancy test (Section 10.7).
- ^k The ongoing AEs from LIN-MD-64 study will be transferred to LIN-MD-66 in the auto-rollover function in EDC.
- ^l Study intervention will be administered in the clinic at the Day 1 Visit (Visit 2). On the day of this visit, all participants must fast for at least 2 hours before arriving at the clinic for their visit, where they will receive their initial dose of study intervention. Participants may eat 30 minutes after dosing (the requirement for linaclotide to be administered 30 minutes prior to any meal at the same time each day will not apply for the first dose). On all other days, it is recommended that participants take linaclotide at approximately the same time each day, 30 minutes before any meal.
- ^m Participants who took their last dose of study intervention in LIN-MD-64 on the day of the EOT Visit and enroll into LIN-MD-66 on that same day will take their first dose of LIN-MD-66 study intervention outside of the clinic at a designated time the following day. Qualified site personnel will complete a follow-up phone call to participants within 48 hours following initial study intervention administration to assess safety.
- ⁿ The number of bottles of study intervention that should be dispensed at each visit is as follows: V2 (1 bottle), V4 (1 bottle), V5 (2 bottles), and V6 (2 bottles). The bottles will be assigned via IWRS.

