The method of recording, evaluating, and assessing causality of AEs and SAEs and the procedures for completing and transmitting SAE reports are provided in [Appendix 3](#).

8.3.3. Method of Detecting Adverse Events, Serious Adverse Events, and Adverse Events of Special Interest

Care will be taken not to introduce bias when detecting AEs and/or SAEs. Open-ended and nonleading verbal questioning of the participant is the preferred method to inquire about AE occurrences.

8.3.4. Follow-up of Adverse Events, Serious Adverse Events, and Adverse Events of Special Interest

After the initial AE/SAE report, the investigator is required to proactively follow each participant at subsequent visits/contacts. All AE/SAE and non-serious AESIs (as defined in [Appendix 3](#)) will be followed until resolution, stabilization, the event is otherwise explained, or the participant is lost to follow-up (as defined in Section [7.3](#)). If a follow-up visit is deemed necessary for appropriate safety surveillance, it will take place within 30 days of the final protocol-defined study visit.

The investigator is obligated to perform or arrange for the conduct of supplemental measurements and/or evaluations as medically indicated or as requested by the sponsor to elucidate the nature and/or causality of the AE or SAE as fully as possible. This may include

additional laboratory tests or investigations, histopathological examinations, or consultation with other health care professionals.

New or updated information will be recorded in the originally completed eCRF.

The investigator will submit any updated SAE data to the sponsor within 24 hours of receipt of the information.

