9.2.1 Treatment-Emergent Adverse Events

An AE will be considered a treatment emergent adverse event (TEAE) if:

- The AE began on or after the date of the first dose of study intervention in LIN-MD-66; or
- The AE was present before the date of the first dose of study intervention in LIN-MD-66 but increased in severity or became serious on or after the date of the first dose of study intervention in LIN-MD-66.

However, an AE that occurs more than 30 days after the last dose of study intervention in LIN-MD-66 will not be counted as a TEAE.

An AE will be considered a treatment emergent serious adverse event (TESAE) if it is a TEAE that additionally meets any serious adverse event (SAE) criterion.

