9.2.4 Treatment-Emergent Adverse Events Exposure-Adjusted Incidence Rate (EAIR)

The EAIR provides exposure adjusted rates for the first occurrence of an event. It is an adjusted incidence rate calculated as 100 times the number of subjects with the specific event divided by the total time at risk (in year) among subjects included in the analysis. For a specific event, subjects with multiple occurrences of the event in the specific analysis period will only be counted once in the numerator. The time at risk for a subject without the specific event is the treatment duration, whereas the time at risk for a subject with the event is defined as the treatment duration up to the start date (inclusive) of the first occurrence of the event (date of first onset of the event – date of first dose + 1). The total time at risk in years (denominator) is calculated as dividing the sum of time at risk in days over all subjects included in the analysis by 365.25. The EAIR per 100 patient-years, calculated as [numerator/denominator]*100, is interpreted as the expected number of subjects with at least one occurrence of the specific event per 100 patient-years of exposure to the study drug.

The EAIR per 100 patient-years will be provided for each AE category in the AE overview summary and for the TEAE summary by SOC and PT.

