9.2.7 Diarrhea Treatment Emergent Adverse Events

The TEAE summary by SOC and PT will be provided for those subjects who had a TEAE of diarrhea, regardless of whether these TEAEs occurred concurrently.

The following information will be summarized for the subjects who had a diarrhea TEAE. Each diarrhea TEAE for each subject shall be counted as a separate event for the summaries described in the first 2 bullets below.

- The number and percentage of subjects with a 1 or more diarrhea TEAE events, with 2 or more diarrhea TEAE events, and with 3 or more diarrhea TEAE events.
- The number and percentage of diarrhea TEAEs with an end date, and ongoing at the end of the study.
- Descriptive statistics for the time to onset of the first diarrhea TEAE. The number and the percentage of subjects with diarrhea TEAE will be summarized by time to onset of first occurrence using the following time intervals: Day 1, Day 2, Day 3-7, Week 2 to Week 11 (for each week), and Week 12 and later.
- The longest duration of diarrhea TEAEs within a subject will be summarized. For those subjects with at least one diarrhea TEAE ongoing at the end of the study, the subject will be counted in the 'Ongoing' category. The number and the percentage of subjects classified according to their longest diarrhea duration or ongoing will be summarized by the following duration intervals: 1 day, 2 days, 3-7 days, 8-14 days, 15-28 days, >28 days, and ongoing. The descriptive statistics for the duration of the longest duration of diarrhea TEAE with an end date for subjects will be presented.

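### The exposure-adjusted rate gives zero or negative time at risk to a TEAE that began before the first LIN-MD-66 dose and then worsened, if its original start date is kept

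*SAP*

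**What the plan says.** SAP 9.2.1 gives two ways for an AE to be treatment-emergent. The first is an onset on or after the first dose: "The AE began on or after the date of the first dose of study intervention in LIN-MD-66; or". The second covers earlier onsets, provided the change comes once dosing in this study has begun: "The AE was present before the date of the first dose of study intervention in LIN-MD-66 but increased in severity or became serious".

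SAP 9.2.4 defines the exposure-adjusted incidence rate (EAIR) from time at risk. Without the event, "The time at risk for a subject without the specific event is the treatment duration". For a participant who has the event, it states: "time at risk for a subject with the event is defined as the treatment duration up to the start date (inclusive"). Its formula for this is "date of first onset of the event – date of first dose + 1". The EAIR is reported for each category of the AE overview and for TEAEs by SOC and preferred term.

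SAP 9.2.7 asks for "Descriptive statistics for the time to onset of the first diarrhea TEAE", and for counts in onset intervals of which the earliest is Day 1.

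The protocol brings lead-in AEs into this study. Table 1-1, footnote k: "The ongoing AEs from LIN-MD-64 study will be transferred to LIN-MD-66 in the auto-rollover function in EDC". Section 10.10.1 has ongoing AEs from the prior study entered in the eCRF. On follow-up, Section 8.3.4 says: "New or updated information will be recorded in the originally completed eCRF".

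**The concern.** The TEAE definition and the time-at-risk formula use different dates. A TEAE admitted by the second criterion matters because of what happened after first dose, but the formula times it by when it began, which is before first dose. Taken literally, the participant adds one event to the numerator and takes time away from the denominator. The rate then no longer has the meaning SAP 9.2.4 gives it, participants with an event per 100 patient-years of exposure.

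The bias runs one way, upward, and weighs most in small cells. SAP 9.1 splits the summaries by intervention group and age group, separately for FC and IBS-C.

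The diarrhea onset table has a related gap. It has no place for a diarrhea that began in the lead-in study and worsened here, if its original onset date is used.

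**Working it through.** **Stated figure.** The documents give no EAIR, so there is none to reproduce. The check applies the SAP formula.

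**Inputs from the documents**
- Time at risk with the event = onset date − first dose date + 1 (SAP 9.2.4).
- Treatment duration = last dose date − first dose date + 1, in this study only (SAP 6.0).
- EAIR = 100 × participants with the event ÷ (total days ÷ 365.25).
- Lead-in length: 12 weeks (84 days) in LIN-MD-64, 4 weeks (28 days) in LIN-MD-63. Participants who enroll on the day of their last lead-in dose take the first LIN-MD-66 dose the next day (Protocol 4.1).

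**Time at risk for one worsened AE that keeps its start date**
- Onset on the first-dose day: 0 + 1 = 1 day.
- Onset the day before: −1 + 1 = 0 days.
- LIN-MD-64 completer, first dose on day 85, onset on lead-in day 1: 1 − 85 + 1 = −83 days. With first dose 28 days after the last lead-in dose (day 112): 1 − 112 + 1 = −110.
- LIN-MD-63 completer, same two cases: 1 − 29 + 1 = −27, and 1 − 56 + 1 = −54.

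An AE that starts during LIN-MD-66 screening and later worsens behaves the same way. In broad categories such as any TEAE, a pre-dose onset also sorts ahead of every post-dose onset, so it sets that participant's time.

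**Effect on the EAIR.** Group sizes, event counts and dates below are assumptions. Treatment lasts 168 days (FC) or 364 days (IBS-C). In example A, events occur on Day 40, and each rolled-over AE began 45 days before first dose (−45 + 1 = −44 days) and worsened on Day 40. In the other examples, events occur on Day 30, and each rolled-over AE has −83 days and worsened on Day 30. Cells show total days and EAIR per 100 patient-years.

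| Example | Date of worsening | Floored at zero | Literal formula |
|---|---|---|---|
| A. FC, 20 participants, 10 events, 1 rolled over | 2,080; 175.6 | 2,040; 179.0 (+2.0%) | 1,996; 183.0 (+4.2%) |
| A. Same, 3 rolled over | 2,080; 175.6 | 1,960; 186.4 (+6.1%) | 1,828; 199.8 (+13.8%) |
| B. FC, 60 participants, 6 events, 1 rolled over | 9,252; 23.69 | 9,222; 23.76 (+0.3%) | 9,139; 23.98 (+1.2%) |
| C. IBS-C, 60 participants, 6 events, 1 rolled over | 19,836; 11.05 | 19,806; 11.06 (+0.2%) | 19,723; 11.11 (+0.6%) |
| D. FC, 60 participants, 36 events, 1 rolled over | 5,112; 257.2 | 5,082; 258.7 (+0.6%) | 4,999; 263.0 (+2.3%) |
| E. FC, 20 participants, 12 events, 3 rolled over | 1,704; 257.2 | 1,614; 271.6 (+5.6%) | 1,365; 321.1 (+24.8%) |
| F. IBS-C, 20 participants, 12 events, 3 rolled over | 3,272; 134.0 | 3,182; 137.7 (+2.8%) | 2,933; 149.4 (+11.6%) |

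For example, A with three rolled-over AEs: 7 × 40 − 3 × 44 + 10 × 168 = 1,828 days = 5.00 patient-years, and 100 × 10 ÷ 5.00 ≈ 199.8.

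The planned minimum of 120 spread evenly over the six arms in Protocol 10.6 would give 120 ÷ 6 = 20 per arm. The documents state no such split.

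**Diarrhea onset.** SAP 9.2.7 gives no formula and no time origin. If the recorded onset date is used, a value of 0 or below precedes the first interval and the case is unclassified.

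**The case against.** **The recording convention is not settled.** Protocol 8.3 and 10.3.1 treat a change in severity of a pre-existing condition as an AE, so a site could open a new record dated at the worsening, and time at risk would be positive. This stands as a limit on certainty. It does not remove the problem. A re-dated AE would already meet the first TEAE criterion, so the second does work only where the earlier start date is kept, and Protocol 8.3.4 points to updating the original record. The detailed table specifications are in a separate document (SAP 1.0) and might contain a rule.

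**Negative time is one reading.** SAP 9.2.4 describes treatment duration up to the start date, and treatment duration begins at first dose, so the words imply zero while the formula gives negative values. Flooring at zero roughly halves the bias in example A and cuts it further in the others. It does not remove it.

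**A reader might infer that such cases are common or the distortion usually large.** The documents do not support that. The AE must be ongoing at entry, then worsen or become serious. Exclusion 1.01 (Protocol 5.2.1) removes some participants with unresolved AEs, at the investigator's judgment. The larger effects need several cases in a small group.

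**A reader might also infer that diarrhea duration should restart at worsening.** That does not follow. Days of diarrhea in the lead-in study are real duration, and restarting the count could hide a prolonged episode.

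**Consequences are bounded.** There is no inferential testing (SAP 11.0), participant counts and percentages are unaffected, and all AEs are listed.

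**Conclusion.** The concern holds for the EAIR and, conditionally, for diarrhea time to onset. The formula in SAP 9.2.4 does not fit the TEAE definition in SAP 9.2.1: a TEAE admitted only by worsening or seriousness, recorded under its original start date and counted as the first occurrence, has time at risk of zero or less. The rate is then too high.

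The likely size is small in large groups and material in small ones. One case among 60 participants adds 0.6% (IBS-C) to 1.2% (FC) on the literal formula with 6 events, and 2.3% in FC with 36 events. Three cases among 20 FC participants add about 6% with flooring and 14% to 25% literally. The IBS-C figures for three in 20 are 2.8% and 11.6%. All rest on assumed group sizes, event counts and dates, and on the start date being kept. How many such cases will occur cannot be judged from the documents. The point warrants correction in the SAP but does not threaten the study's main safety counts.

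**What to change.** Add to SAP 9.2.4, and to the time-to-onset item in SAP 9.2.7:

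*For a TEAE with onset before the first LIN-MD-66 dose, the event date is the date on which it first increased in severity or became serious on or after that dose. If that date is not recorded, the first dose date is used. No participant contributes less than 1 day at risk.*

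Apply the substitution before selecting each participant's first occurrence. Keep diarrhea duration based on the actual start date, and flag episodes that began before the first LIN-MD-66 dose.

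The cost is a few sentences and a small programming change. No eCRF change is required. The downside is that the fallback leaves some upward bias where no worsening date is recorded. In example A with three such cases, 7 × 40 + 3 × 1 + 1,680 = 1,963 days, and 2,080 ÷ 1,963 = 1.060, so the rate is still 6.0% too high. A table footnote giving the number of TEAEs dated by the fallback would let a reader judge this.

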9.2.5 SAEs (Including Deaths) and Adverse Events Leading to Study Drug Discontinuation

Summary tables will be provided for participants with TESAEs and participants with TEAEs leading to study discontinuation if 5 or more participants reported such events.

SAEs (including deaths) and AEs leading to study drug discontinuation will be listed.

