6.3. Measures to Minimize Bias: Randomization and Blinding

Participants with FC, 12 to 17 years of age, will be randomly assigned at a 1:1 ratio to 72 µg linaclotide or 145 µg linaclotide.

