6.6. Dose Modification

At the discretion of the investigator, any participant who experiences an AE intolerable enough to prompt a consideration of study withdrawal may receive a temporary suspension of dosing. The duration of a dosing suspension will be at the investigator's discretion; however, after a participant has been off study intervention for 3 days, or if the participant requires a suspension of dosing on more than 1 occasion, the investigator must contact the sponsor to discuss the participant's continued participation in the study.

Participants who experience an intolerable AE that may be related to the use of linaclotide can be dose reduced one dose level only during the course of the study at the investigator's discretion as shown in [Table 6-1](#). Subsequent dose adjustments (between the initial dose and reduced dose) are also permitted at the investigator's discretion. Participants receiving blinded linaclotide treatment will be dose adjusted in a blinded fashion via IWRS.

Table 6-1 Dose Reductions

	IBS-C				FC	
	Open-label (µg)		Blinded (µg)		Open-label (µg)	
Initial dose	290	145	290	145	145	72
Reduced dose	145	72	145	72	72	N/A

The decision of whether to temporarily suspend dosing or dose reduce following the occurrence of an intolerable AE is per the investigator's discretion.

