7.1.1. Removal of Individual Participants from Therapy or Assessment

Participants **must** be prematurely discontinued from the study for reasons of safety including those who experience:

- An SAE considered by the investigator or the sponsor to be possibly related or related to study intervention
- An AESI (evidence of significant volume depletion and/or significant electrolyte and/or ECG abnormalities that are considered by the investigator or sponsor to be related to diarrhea) related to the study intervention (ie, treatment-related AESIs)
- Pregnancy
- Presence of intentional overdose or intentional misuse per investigator discretion
- The occurrence of any other AE that in the opinion of the investigator or the sponsor is possibly related or related to the study intervention that represents a clinically significant safety risk to the participant

Participants **may** also be prematurely discontinued from the study for reasons of safety including those who experience:

- A vital sign, ECG, and/or laboratory abnormality judged to be clinically significant by the investigator and that, in the opinion of the investigator or the sponsor, is possibly related or related to the study intervention

- An intolerable AE (defined as an AE that subjectively would cause a patient to consider study withdrawal), see Section 8.3

Additionally, discontinuation of study intervention for abnormal liver function should be considered by the investigator when a participant meets the criteria for Hy's law or the appearance of abnormal laboratory test results suggesting severe drug-induced liver injury (DILI) (refer to [Appendix 9](#)), or if the investigator believes that it is in best interest of the participant.

All enrolled participants who prematurely discontinue from the study, regardless of cause, are required to return for the EOT study assessments. The EOT assessments are defined as completion of the evaluations scheduled for all participants.

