9.2.2 Adverse Event Overview

Overall summary of TEAEs will be provided on a per-participant level for TEAEs, treatment-related TEAEs, TESAEs, deaths, and TEAEs leading to study intervention discontinuation.

If there is more than one event for the same participant, the participant will be counted only once.

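### AE discontinuation is the only planned adverse-event output tied to an action on study drug, so it can understate how many children could not stay on their assigned dose, and can do so unevenly between the randomised FC arms

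*SAP*

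**What the plan says.** Under Protocol 6.6, "any participant who experiences an AE intolerable enough to prompt a consideration of study withdrawal may receive a temporary suspension of dosing". Participants whose intolerable AE may be related to linaclotide "can be dose reduced one dose level only during the course of the study". The choice between the two is left to the investigator. Table 6-1, repeated in SAP 2.3, gives a reduced dose for every IBS-C group and for FC 145 µg (to 72 µg), and N/A for FC 72 µg. Protocol 7.1.1 defines an intolerable AE as one that would make a patient consider leaving the study. It lists such an AE among the reasons for which a participant may, not must, be discontinued.

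On randomisation, Protocol 6.3 states: "Participants with FC, 12 to 17 years of age, will be randomly assigned at a 1:1 ratio", to 72 or 145 µg. This is the study's only randomised comparison (Protocol 10.6).

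On reporting, the overview in SAP 9.2.2 covers "TEAEs, treatment-related TEAEs, TESAEs, deaths, and TEAEs leading to study intervention discontinuation". SAP 9.2.5 adds a summary table of "participants with TEAEs leading to study discontinuation if 5 or more participants reported such events", plus a listing; Protocol 9.4.1 plans the same table. Dose change enters the SAP's analysis rules only in 4.0. There, a participant whose dose changed is grouped by the dose received for most of the intervention period, with ties going to the higher dose.

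**The concern.** The children for whom suspension or reduction is offered are the same children who would otherwise enter the AE-discontinuation row. A child who could not tolerate the assigned dose, was stepped down and stayed in the study is absent from that row, and no other planned output identifies that child as having changed dose because of an AE.

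The route out of that row is also unequal between the arms to which FC adolescents are randomised: one arm has a step-down and the other has none. Long-term safety is the study's only objective and its output is entirely descriptive. A reader setting the 72 and 145 µg columns side by side could therefore take a difference in available options for a difference, or a lack of difference, in how well the doses are tolerated.

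**Working it through.** **No plan figure to reproduce.** The only planning number is enrolment of at least 120, which SAP 2.4 says has no statistical basis. SAP 11.0 rules out inferential testing. The documents give no rates of intolerance, reduction or suspension for this study, so every rate below is an assumption.

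**Routes and where they are reported**

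| Response to an intolerable AE | FC 72 µg | FC 145 µg | IBS-C groups | Counted in the SAP text |
|---|---|---|---|---|
| Discontinuation | yes | yes | yes | 9.2.2, 9.2.5 |
| Suspension | yes | yes | yes | no |
| One-level reduction | no | yes | yes | no |

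**Do other planned outputs recover the missing counts?**
- Duration (SAP 6.0) is last dose date minus first dose date plus 1, so a suspension inside that span disappears.
- Compliance (SAP 6.0) is capsules taken over capsules expected. A child fully adherent to a lower strength looks fully compliant, and a suspension could not be told apart from missed doses.
- Severity (SAP 9.2.3) is not intolerance. In LIN-MD-62 no diarrhea was severe, yet a 12- to 17-year-old on Dose C stopped for moderate diarrhea (Protocol 2.2.2). At that age Dose C was 72 µg (Table 2-1).

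**Effect on the FC comparison, by assigned dose.** Let π be true intolerance, u the share of cases kept on by suspension, and s the share of the remaining 145 µg cases kept on by reduction.

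- Discontinuation at 72 µg = π₇₂(1 − u₇₂)
- Discontinuation at 145 µg = π₁₄₅(1 − u₁₄₅)(1 − s)

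With equal π and equal u, the 145:72 ratio is 1 − s, whatever π and u are: 1.00, 0.75, 0.50 and 0.25 at s = 0, 0.25, 0.50 and 0.75. With π = 10%, u = 0 and s = 0.5, the row shows 10.0% at 72 µg and 5.0% at 145 µg. A true ratio k in favour of 72 µg is hidden when k(1 − s) = 1: s = 1 − 1/1.5 = 0.33 for k = 1.5, and s = 1 − 1/2 = 0.50 for k = 2.

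**Dependence on suspension.** With equal π, the ratio is (1 − u₁₄₅)(1 − s)/(1 − u₇₂). With s = 0.5 and u₁₄₅ = 0.25, the numerator is 0.75 × 0.5 = 0.375, so the ratio returns to 1 when u₇₂ = 1 − 0.375 = 0.625. Much heavier use of suspension at 72 µg would cancel the effect.

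**Effect of the SAP 4.0 grouping.** Take 30 per arm, true intolerance of 20% at 145 µg and 10% at 72 µg, u = 0, s = 0.5, and all reductions made before the midpoint (168/2 = day 84) and kept.
- 145 µg: 30 × 0.20 = 6 cases, of which 3 are reduced and 3 stop.
- 72 µg: 30 × 0.10 = 3 stop.
- By assigned dose: 3/30 = 10% in both arms.
- By majority dose: 3/(30 − 3) = 11.1% against 3/(30 + 3) = 9.1%.
- Children who stopped or were reduced, by assigned dose: 6/30 = 20% against 3/30 = 10%.

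The smaller denominator moves the 145 µg discontinuation rate up slightly, but the two-fold difference stays hidden. In addition, the AEs of the 3 reduced children, which occurred on 145 µg, now appear in the 72 µg column.

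**The case against.** The strongest reply is that the plan has much more than a discontinuation row. It covers TEAEs by severity, related TEAEs, exposure-adjusted rates, AESIs, and diarrhea recurrence, onset and duration (SAP 9.2.3 to 9.2.7). A reader might infer that discontinuation is the SAP's only tolerability measure, or that a reduced child counts as a success. The documents support neither. That child's TEAE is still counted, graded and listed, and nothing in the SAP calls it a success. The stated objective is safety, with no separate tolerability endpoint. What is missing is narrower: the link from the AE to the dose change.

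A reader might also infer that the FC contrast is biased towards 145 µg as a matter of fact. That goes too far. Reduction and suspension are discretionary, stopping remains allowed, and Protocol 7.1.1 requires it for some events. Suspension is open to both arms and may be used more where it is the only alternative. No contrast is tested.

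Nor can a reversal of the arms be presented as expected. Assume intolerance of 15% at 145 µg and 8% at 72 µg, 100 per arm, no suspension and early reductions. If 7 of the 15 are reduced, the SAP 4.0 grouping gives 8/93 = 8.6% against 8/107 = 7.5%. If 9 are reduced, it gives 6/91 = 6.6% against 8/109 = 7.3%. The order changes only in the second case, by 0.7 points, on invented rates. The lead-in summaries mention 1 linaclotide discontinuation for diarrhea among 132 (LIN-MD-62) and 1 linaclotide AE discontinuation among 82 (LIN-MD-63). Those studies lasted 4 weeks, mostly at lower doses. At 2/214 = 0.9%, an arm of 30 would expect about 0.3 events, and any difference would be noise.

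Two practical points also stand. Table specifications sit in a separate document that was not available, and the documents do not show that the AE behind each dose change is recorded.

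**Conclusion.** The gap is real and modest. AE discontinuation is the only AE output in the SAP text defined by an action on study drug. It can understate how many children could not stay on their assigned dose in any group where suspension or reduction is used.

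For FC adolescents, the descriptive side-by-side reading of this row can favour 145 µg, because only that arm has a step-down. That direction assumes suspension is used similarly in both arms. The size cannot be found from the documents; on assumed values it runs from no effect (s = 0) to a ratio of 0.25 (s = 0.75) at equal true intolerance. The majority-dose rule adds to this by moving children reduced early, with their AEs on 145 µg, into the 72 µg group. No planned test is affected, because there is none. The 5-participant condition limits only the 9.2.5 summary tables, not the overview or the listings.

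**What to change.** Reporting only; no dosing rule changes.

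- In SAP 9.2.2 and 9.2.5, add per-participant counts of TEAEs leading to dose reduction, to suspension of dosing, and to any of reduction, suspension or discontinuation.
- Show these by initially assigned dose, alongside the SAP 4.0 grouping. Show randomised FC adolescents separately; the SAP's FC 12 to 18 age group already provides the place.
- Footnote the discontinuation row to say that Table 6-1 gives no reduced dose for FC 72 µg.
- Use one term for discontinuation. SAP 9.2.2 refers to study intervention, the 9.2.5 heading and listing to study drug, and the 9.2.5 table text to the study.
- Have the sponsor confirm that the eCRF links each reduction or suspension to the AE that caused it. SAP 6.0 cites an exposure form, and Protocol 6.6 mentions IWRS dose adjustment only for blinded participants; neither shows that link.

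The cost is SAP wording and a few tables, if the link is recorded. The reported figures will look somewhat less favourable than discontinuation alone.
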